10.0 Data and Specimen Banking

10.1 Storage of specimens.

Muscle specimens and blood specimens for long-term storage will be stored in a freezer belonging to [name] research program at Northwestern University, in the freezer farm in the basement of Olson Pavilion.

Specimens will be stored for up to 70 years, after which they will be destroyed.

10.2 Data to be stored or associated with each specimen.

Specimens will be coded; meaning that a key will exist that can link the codes back to the direct subject identifiers. Each participant will be assigned a unique study ID number that can be traced back to the study participant. The muscle specimens and the blood samples that are stored will be labeled with this unique identifier and the date and time of the blood collection.

10.3 Procedures to release data or specimens.

Only [name] has control over release of study data or specimens. Any investigators seeking to analyze blood or muscle specimens must contact [name] for permission. Each request, if it occurs, will be considered on a case-by-case basis. [name] will obtain IRB approval prior to releasing any blood or muscle specimens for analysis, other than those tests specifically named in this application.

11.0 Data and Specimen Management

11.1 Data management.

Data is recorded using preprogrammed instruments and an electronic case report form using secure, HIPAA-compliant REDCap database software on servers maintained by Northwestern's Clinical and Translational Sciences Institute. We have substantial experience with REDCap.

11.2 Power Estimates/Calculations.

The COCOA-PAD Study is a pilot study intended to collect preliminary data to estimate an effect size and to assess the feasibility of our proposed methods. Therefore, we calculated the sample size that allows us to identify an effect size estimate. Our power calculations anticipate a < 10% drop-out rate at 6-month follow-up, based on data from our completed GOALS and SILC randomized trials in PAD participants (34,60). For our primary aim, we will compare changes in six-minute walk performance at 6-month follow-up between the epicatechin-rich cocoa group and the placebo group. Comparisons will be made for measures obtained both while off of the study beverages for 2.5 hours and while off of the study beverages for 24 hours, respectively, in order to assess both acute and chronic effects of cocoa on six-minute walk. A total of 40 participants completing the trial will provide a two-sided 95% confidence interval (CI) with a margin of error of 0.64 standard deviation (SD) for the effect size in change of six-minute walk performance between the cocoa (n=20) and the placebo groups (n=20). Using the estimated SD from our SILC trial (34), the margin of error of 0.64 SD represents approximately 33 meters. Prior studies have defined clinically meaningful changes in the six-minute walk as 20 meters (small meaningful difference) and 50 meters (large meaningful difference) (73,74). Similarly, 40 participants completing the trial provides a two-sided 95% CI with a margin of error of 0.64 SD for the effect size in 6-month change of each secondary outcome between the cocoa and placebo groups.

Statistical Analyses. Data will be analyzed according to each participant's originally assigned group, irrespective of whether the participant adheres to his/her assigned group (i.e. intention to treat principle). For our Primary Aim, we will use a t-distribution to obtain the 95% CI for the difference in changes in six-minute walk performance at 6-month follow-up between the

cocoa and placebo groups. Comparisons at six months will be made to measure both the acute effects (2.5 hours after drinking the study beverages) and the chronic effects (24 hours after drinking the study beverages). The characteristics of participants in the intervention and control group will be compared using t or chi-square tests. If there is indication of major imbalance, we will perform analysis of covariance (ANCOVA) with change in six-minute walk distance as the response variable to evaluate differences between the two groups, adjusting for potentially imbalanced covariates. If there is evidence that the normality assumption for the distribution of outcome measures is violated, we will either apply appropriate transformation to the original measures before conducting the aforementioned analyses or obtain a nonparametric estimate and 95% CI for the difference in median between the cocoa and placebo groups (74). These methods will also be used to analyze outcomes in our secondary specific aims.

11.3 After recruitment was completed, and prior to reviewing results, investigators determined that a one-sided test with a significance level of 0.10 will be used to in the statistical analyses. Correspondingly, the point estimator and one-sided 90% CIs will be obtained for the differences in all outcomes between the cocoa and the placebo groups. Since the trial is a pilot study collecting preliminary evidence on the potential benefit of epicatechin-rich cocoa on change in walking ability and other outcomes in PAD patients, one-sided tests are justified. For the same reason, the decision on whether a larger independent confirmatory study is warranted to prove the hypothesized treatment effect of cocoa will be made based on all relevant evidence in this pilot study collectively, which include but are not restricted to the statistical significance. Steps to secure data to maintain confidentiality during storage, use, and transmission.

First, all research assistants must complete training in protection of subject privacy and prevention of disclosure of identifying information.

Second, all data collection forms are maintained in a secure office space.

Third, our study databases are maintained in locked computer files or on secure hard-drives that are password protected; to which only authorized staff have access. [name] or a study manager must provide permission for programmers and research assistants to access study databases.

Fourth, a study identification number will be assigned to each participant. This identification number will be used to label blood specimens, for example. In addition, most pages of our data collection forms will have only the study identification number listed (and not the participant's name, for example).

11.4 Quality Control.

Health interviewers will be trained by a senior coordinator and certified by [name] in each data collection element, using a detailed checklist. Health interviewers are rigorously evaluated for adherence to protocol, delineated in our manuals, prior to beginning data collection. They are re-certified approximately every six months by a project manager or [name]. When deficiencies are identified, interviewers undergo additional training and re-assessment. Ten percent of participants are randomly identified for quality control. This subset has their ABI measured twice by independent examiners and may have a split sample of muscle tissue (i.e. two samples from the same participant) sent for analyses. The second muscle sample is designated an arbitrary identification number to which the technician is blinded. Thus, quality control is monitored continuously. A 20% subset of collected MR images will be interpreted by two independent evaluators. For the skeletal muscle measures, a 10% subset of participants will have an additional quality control muscle specimen analyzed. To achieve this, up to 40% of individuals may have up to 400 mgs of tissue removed.

Blinding for data collection. The study design is double-blinded. Participants, study investigators, and the study coordinator collecting outcome data will be unaware of group assignment.

Missing Data. First, missing data may occur if participants are lost to follow-up. However, in our prior randomized trials of PAD participants, drop-out rates were <10% at 6-month follow-up (34,60,75). Thus, drop-out should be small. Second, we recognize that not all participants may return for a second muscle biopsy at follow-up. However, 95% of participants who completed a muscle biopsy in our pilot study indicated that they were willing to return for a second biopsy. Thus, loss to follow-up should be small. Third, some participants may not adhere to their beverage. We will measure adherence and will perform a sensitivity analysis that includes only those who adhered to 80% or more of their assigned beverage. This pilot study will determine likely adherence rates for a larger trial.

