The COCOA-PAD Study is a pilot double-blind, randomized controlled trial to test our hypothesis that epicatechin-rich cocoa improves endothelial function, increases calf skeletal muscle mitochondrial function and biogenesis, and favorably alters skeletal muscle levels of myostatin, follistatin, and mitochondrial transcription factor-alpha (TFAM), thereby improving lower extremity functioning in older people with PAD. If our proposed pilot study supports our hypotheses, results will be used to design a large, definitive randomized clinical trial of epicatechin-rich cocoa in older people with PAD.

Forty-four participants with PAD age 60 and older will be randomized to epicatechin-rich cocoa vs. an epicatechin-free and cocoa-free placebo (matched in appearance and taste) daily for six months. Our primary

outcome is the six-minute walk, a well-validated measure of walking endurance in PAD (32-34). Secondary outcomes are pain-free and maximal treadmill walking performance, brachial artery flow-mediated dilation (FMD), accelerometry-measured physical activity, calf muscle biopsy measures, and MRI-measured calf muscle perfusion. To distinguish between the acute vs. chronic effects of cocoa, the six-minute walk and brachial artery FMD measures will be obtained while off of study beverages for 2.5 hours (acute) and 24 hours (chronic), respectively. . The treadmill stress test will be measured while off of study beverages for 48 hours. Remaining outcomes will be measured while still taking study beverages whenever possible.

Primary Aim. Among 44 participants with PAD age 60 and older, we will determine whether epicatechin-rich cocoa daily for six months improves six-minute walk performance compared to placebo.

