8.0 Study Endpoints

The primary study endpoint is the six-month change in the six-minute walk data.

Secondary study endpoints include a) six-month change in maximal and pain-free treadmill walking time; b) six-month change in brachial artery FMD; c) six-month change in accelerometer-measured physical activity; and d) six month change in the following calf skeletal muscle measures: activity of Cytochrome C Oxidase (COX) and citrate synthase, calf muscle levels of peroxisome proliferative activated receptor- γ co-activator 1 α (PGC-1 α), capillary density, myostatin, follistatin, and mitochondrial transcription factor-alpha (TFAM)

Data will be collected at baseline and at the 6-month follow-up visit.

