The six-minute walk and brachial artery FMD will be measured while off of study beverages for 2.5 hours and 24 hours, respectively. . The treadmill stress test will be measured while off of the study beverages for 48 hours. The calf muscle biopsy will be performed after other outcome measures are complete and while on study beverages whenever possible. If extenuating circumstances prevent outcome measurement in these defined time frames, the measurement will be obtained as close as possible to the desired time point/length of time after the final cocoa dose.

Some or all study measures may be repeated at baseline or follow-up for data quality (e.g. if a treadmill test must be stopped due to extremely high blood pressure before the patient completed the test is one potential example of why a measure may need to be repeated).

In some cases, participants may be asked to take study beverages for longer than six months. For example, if a participant has an illness that prevents them from returning at six months for follow-up testing or if they are out of town during their six-month follow-up window. In these instances, participants will be asked to continue taking their study beverages for more than six months. Participants may be asked to take up an additional two months of study beverages.

9.2 *Research procedures.*

Ankle Brachial Index (ABI). After the participant rests supine for five minutes, the right brachial, dorsalis pedis (DP), posterior tibial (PT) and left DP, PT, and brachial artery pressures are measured using a hand-held Doppler probe. Pressures are measured twice. The ABI is calculated for each leg by dividing the average of the DP and PT pressures by the average brachial pressure (59). If a participant qualifies for a heel-rise ABI based on their initial ABI, they will be asked to perform 50 heel-rises at a rate of one per second followed by additional measurements of the right and left brachial, DP, and PT pressures.

Questionnaire Administration. Participants will be administered IRB-approved study questionnaires by a trained and certified study coordinator.

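### The 2.5-hour six-minute-walk comparison is labelled the acute effect, but after six months of daily beverage it estimates the total effect, and the contrast that would isolate the acute part is not planned

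*Combined protocol and SAP*

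**What the plan says.** Section 1.1 gives the reason for two off-beverage times: "To distinguish between the acute vs. chronic effects of cocoa". It then says that the six-minute walk and brachial artery FMD "will be obtained while off of study beverages for 2.5 hours (acute) and 24 hours (chronic), respectively".

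Section 11.2 (Power Estimates/Calculations) applies both times to the walk. It begins "Comparisons will be made for measures obtained both while off of the study beverages for 2.5 hours", adds the 24-hour measure, and gives the purpose as "in order to assess both acute and chronic effects of cocoa on six-minute walk". The Statistical Analyses paragraph of Section 11.2 attaches the labels: "Comparisons at six months will be made to measure both the acute effects (2.5 hours after drinking the study beverages) and the chronic effects", with the chronic effects taken at 24 hours. Each comparison is a between-arm difference in change from baseline with a t-based interval. Section 11.3 later replaces the two-sided intervals: "the point estimator and one-sided 90% CIs will be obtained for the differences in all outcomes between the cocoa and the placebo groups".

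On the schedule, Section 8.0 says "Data will be collected at baseline and at the 6-month follow-up visit". Under Section 3.1, baseline testing decides eligibility for randomization, so it precedes any study beverage. Section 9.1 says of follow-up: "The six-minute walk and brachial artery FMD will be measured while off of study beverages for 2.5 hours and 24 hours, respectively".

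No section plans the 2.5-hour minus 24-hour difference, an interval for it, or a rule for reading the two comparisons together.

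**The concern.** A change score from a pre-randomization baseline to a walk 2.5 hours after a drink, at the end of six months of daily drinks, contains everything the beverage has done by then. It includes any lasting benefit as well as any short-lived gain from the latest dose, so the between-arm difference is a total effect. The 24-hour comparison is the chronic effect plus any residual of the last dose. Only the difference between the two isolates the recent-dose increment.

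The labels therefore do not match what is estimated, and the comparison called acute cannot make the distinction that Section 1.1 wants. A benefit that is wholly chronic and one that is wholly acute could give the same 2.5-hour result and would carry the same label.

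At stake is what the pilot can say about whether benefit depends on a recent dose, which bears on when a definitive trial should measure the walk. Section 11.3 bases the decision on a larger study on all the evidence together, so this point does not decide that by itself.

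**Working it through.** **1. What each comparison contains.** Let C be the between-arm effect still present at 24 hours off beverage, and A the further effect present at 2.5 hours.

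- 24-hour comparison: C
- 2.5-hour comparison: C + A
- Increment: (C + A) − C = A

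Illustration: with 40 m at both times, the plan reports a 40 m acute effect although A = 0. With 40 m at 2.5 hours and 0 m at 24 hours, it again reports a 40 m acute effect, and A = 40 m.

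**2. The plan's own precision (Section 11.2).** With 20 per arm and 38 df:

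- Two-sided 95% margin: t(0.975) × √(2/20) = 2.024 × 0.316 = 0.640 SD. This reproduces the stated 0.64 SD.
- The plan equates 0.64 SD with about 33 m, so SD = 33/0.64 = 51.6 m and SE = 51.6 × 0.316 = 16.3 m.
- One-sided 90% margin (Section 11.3): 1.304 × 16.31 = 21.3 m.

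**3. How often a purely chronic effect is reported as acute.** Take A = 0 and test at one-sided 0.10. Power is from the noncentral t with noncentrality C/16.31. The values 20 m and 50 m are the plan's small and large meaningful differences; 33 m is its margin.

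| Chronic effect C | Comparison labelled acute is positive |
|---|---|
| 20 m | 0.47 |
| 33 m | 0.76 |
| 50 m | 0.96 |

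This is ordinary power for a real total effect. The error lies in the label.

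**4. Comparing the two test results is no substitute.** Simulation of 200,000 trials per row: bivariate normal changes, the same chronic shift at both times, A = 0, and an assumed correlation of 0.8 between the two change scores.

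| C | Both positive | 2.5 h only | 24 h only | Neither |
|---|---|---|---|---|
| 20 m | 0.37 | 0.10 | 0.10 | 0.42 |
| 33 m | 0.69 | 0.08 | 0.08 | 0.16 |
| 50 m | 0.94 | 0.02 | 0.02 | 0.02 |

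At 20 m, about one trial in five is positive at exactly one time although there is no acute effect. The paired contrast is positive in 0.10 of these trials, its nominal rate.

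**5. Precision of the paired contrast.** For each participant take D = month-6 walk at 2.5 hours minus month-6 walk at 24 hours. If one baseline walk serves both changes, baseline cancels. With equal SDs at the two times and correlation ρ:

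- SD(D) = 51.56 × √(2(1 − ρ))
- One-sided 90% margin = t × SD(D) × √(2/n), with t = 1.304 (n = 20 per arm, 38 df) or 1.310 (n = 16 per arm, 30 df)

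| ρ (assumed) | SD(D) | Margin, 20 per arm | Margin, 16 per arm with both walks (assumed) | Power for A = 20 m, 20 per arm |
|---|---|---|---|---|
| 0.5 | 51.6 m | 21.3 m | 23.9 m | 0.47 |
| 0.7 | 39.9 m | 16.5 m | 18.5 m | 0.61 |
| 0.8 | 32.6 m | 13.4 m | 15.1 m | 0.74 |
| 0.9 | 23.1 m | 9.5 m | 10.7 m | 0.92 |

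Power is from the noncentral t with noncentrality 20/(SD(D) × √0.1) and assumes no residual at 24 hours.

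A reader holding only the two planned intervals does not know ρ. Over correlations from 1 down to 0, the margin of the subtraction runs from 0 m to 1.304 × 16.31 × √2 = 30.1 m. The point value can be had by subtraction among participants with both walks; the interval cannot.

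**6. Whether both walks are required.** In Sections 1.1 and 9.1, *respectively* can pair the walk with 2.5 hours only and FMD with 24 hours only. Section 11.2 compares the walk at both times. The contrast needs both walks in the same participants, so this wording matters here.

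**The case against.** The labels can be read as timing labels, since each is defined by hours off beverage. Both estimates would be reported side by side, so equal values at the two times would show an attentive reader no recent-dose gain. The acute increment is not an aim, hypothesis or endpoint: the Primary Aim, the first hypothesis and Section 8.0 all concern the six-month effect of daily cocoa. The 24-hour comparison already delivers the chronic part, apart from any residual. The contrast figures rest on correlations that the documents do not supply, and at 0.5 the contrast is no more precise than a single time point. The contrast also adds a third interval on the primary outcome.

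Much of this stands. Both planned estimates are valid, the sample size is unaffected, the chronic comparison is largely sound, and the correlations are assumptions. Section 9.1 also allows tests to be done as near as possible to the intended time, so actual intervals off beverage may vary.

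The timing-label reading does not stand. Sections 1.1 and 11.2 give separating and assessing the two effects as the purpose of the two times, so the labels are claims about what is measured. Side-by-side point estimates give no interval for the difference, and step 4 shows how easily a split result arises without any acute effect.

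**Conclusion.** The concern holds. The 2.5-hour comparison is a total effect labelled as acute, and the contrast that would separate the two effects is absent, along with its interval and interpretation. A purely chronic effect of 20 to 50 m would appear as a positive acute result with probability 0.47 to 0.96. These probabilities rest on the implied SD of 51.6 m, 20 completers per arm and the one-sided 0.10 test. The contrast's margin of 9.5 to 21.3 m rests further on assumed correlations of 0.9 to 0.5 and on equal SDs at the two times.

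The contrast has its own limit. It estimates the recent-dose effect in people who have taken the beverage for six months, net of anything left at 24 hours. With testing only at baseline and month 6, an acute effect in unexposed participants cannot be estimated. The point should be fixed, but it is a fault of labelling and analysis and does not threaten the trial's validity.

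**What to change.** 1. In Section 11.2, call the 2.5-hour comparison the total (chronic plus acute) effect. Keep the 24-hour comparison as the chronic effect, subject to any residual at 24 hours.
2. Add the between-arm difference in each participant's month-6 2.5-hour minus 24-hour distance, with its one-sided 90% CI. Describe it as the recent-dose effect in chronic users, net of any residual at 24 hours. Rank it as supportive, and report actual times off beverage.
3. Reconcile Sections 1.1 and 9.1 with Section 11.2 so that the walk is plainly required at both times. If the 24-hour walks were not collected, report the 2.5-hour result as a total effect and make no acute-versus-chronic claim.

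A smaller matter: no primary time point is named for the walk. If results are still unseen, one could be designated.

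The cost is SAP wording and one paired analysis of walks that Section 11.2 already calls for. The exclusion criteria in Section 3.2 already rule out people unwilling to make three final visits within a week. The downsides are that participants missing either walk drop out of the contrast, and that at a correlation of 0.5 it is no more precise than one time point.

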Randomization. Participants will be randomized to either epicatechin-rich cocoa intervention or placebo using a SAS computer program. We will use block randomization with block sizes randomly selected from 4 and 6 to ensure balance. Randomization will be stratified according to baseline six-minute walk performance.

Monthly assessments to monitor adherence. Participants will attend monthly study visits to receive their monthly supply of beverages.

Participants will be asked to bring any remaining beverage packets from the previous month. Packets will be counted and the number of packets remaining from the previous month will be recorded. Participants will be asked to keep a log of their study beverage consumption and will be asked to turn in their log at each monthly visit. Participants will be asked to bring their current medications to these monthly meetings and changes in medication from the previous month will be recorded. In addition, weight and blood pressure will be measured at each monthly visit. If participants are having difficulty adhering to the beverages, staff may call participants in between monthly visits to check in on adherence and to remind them to fill out their monthly adherence log.

Monitoring diet and weight gain. Participants will receive a handout about monitoring and controlling their weight during the study. Participants in the intervention and control groups will be asked to weigh themselves approximately daily and record their weight on a data collection form. Participants who do not have access to a scale will be provided with a scale. They will be asked to bring this weight chart to each monthly visit. Participants observed to gain five percent or more of their body weight compared to baseline during the study will be evaluated by the study team for possible causes of weight gain. If the weight gain is determined due to increased caloric intake (rather than fluid weight gain), they will receive dietary counseling in effort to avoid additional weight gain and to advise them on dietary methods to help with weight control. Study beverages will be reduced or discontinued if a participant gains 20 or more pounds during the study.

Six-month follow-up testing. After six months of participation in the study, participants will be asked to return for follow-up testing. All measures and tests that were conducted at baseline will be repeated.

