Six-minute walk. Participants will be asked to walk back and forth along a 100-foot hallway for six minutes. They will be instructed that the purpose of the six-minute walk test is to measure the distance they can walk in six-minutes. A script will be read to describe the study procedure. Participants will be asked whether they feel the test is safe to try and whether they have any questions. Participants who cover a distance of less than 500 feet or more than 1600 feet during the baseline six-minute walk will be excluded from the study. In a pilot study to determine whether the six-minute walk distance is longer if a participant uses a 60 foot course instead of a 100 foot course, a subset of participants may be asked to return to the medical center on a separate day in order to perform the six-minute walk test using a 60 foot course. Note that this additional testing will not be performed within a month before the six-minute walk test performed as the primary outcome measure. Only the six-minute walk test performed on the 100 foot course will be used for the study's primary outcome measure.

Treadmill testing. The Gardner graded treadmill exercise test is the standard, accepted treadmill protocol for measuring change in maximal treadmill walking time in response to interventions among PAD participants (34,60,61-63). In the Gardner exercise protocol, speed is maintained at 2.0 miles per hour (mph) and treadmill grade increases by 2.0% every two minutes. If patients cannot walk at 2.0 mph, treadmill speed is started at 0.50 mph and increased by 0.50 mph every 2 minutes until the participant reaches 2.0 mph, after which the treadmill grade is increased every two minutes (34,60,61-63). The treadmill stress test results will be read by the study

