changes in response to epicatechin-rich cocoa administration. Immunohistochemistry will be performed using well standardized, validated methods with excellent test re-test reliability (78,79). Nitro-tyrosine and 4-hydroxynonanal will be measured using Standard Western Blot techniques as described previously (80,81).

Other measures related to skeletal muscle quality and function may also be performed at Northwestern or at other institutions as designated by the Principal Investigator.

MRI. We will use arterial spin labeling with cardiovascular magnetic resonance imaging, methods developed by co-investigator [name] and successfully implemented at Northwestern, to measure changes in calf skeletal muscle perfusion at 3 Tesla between PAD participants receiving epicatechin-rich cocoa vs. placebo. A thigh cuff is inflated in the leg with lowest ABI up to 250 mm Hg. After five minutes, the blood pressure cuff is rapidly deflated. Seven control-tagged image pairs are acquired over 60 seconds using PASL pulse sequence with single-shot echo-planar imaging readouts (field of view 200x200 mm, matrix 64x64, repetition time 4000 ms, echo time 32 ms, slice thickness 10 mm). Perfusion is measured and quantified on a Siemens Healthcare workstation by selectively drawing regions of interest of the hyperemic areas on the perfusion maps.

For pilot data collection, we will obtain MR images that allow us to quantify skeletal muscle and fat in calf muscle of participants.

Medications. Participants and their physicians will be asked not to change their medications during the study if possible. Participants will be asked to bring all of their medications to baseline and follow-up visits and to monthly adherence visits. We will systematically record names and doses of medications and inquire about medication changes at each of these visits. If we find differences in the use of specific medications between study groups (such as statins or cilostazol), we will adjust for these differences.

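### Randomisation is stratified by baseline six-minute walk, but the primary analysis does not adjust for it, and ANCOVA depends on an imbalance trigger that is not defined

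*Combined protocol and SAP*

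**What the plan says.** Section 9.1 (Randomization) states: "Randomization will be stratified according to baseline six-minute walk performance". The number of strata and the cut-points are not given. Section 8.0 defines the primary endpoint as the six-month change in the walk.

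For the primary aim, section 11.2 says "we will use a t-distribution to obtain the 95% CI for the difference in changes in six-minute walk performance" between the cocoa and placebo groups, at both 2.5 and 24 hours after the study beverage. No covariate is named. Participant characteristics are then compared by t or chi-square tests, and the plan continues: "If there is indication of major imbalance, we will perform analysis of covariance (ANCOVA") on change, adjusting for whichever covariates look imbalanced. For the other outcomes: "These methods will also be used to analyze outcomes in our secondary specific aims".

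Section 11.3 alters the inference but not the model: "After recruitment was completed, and prior to reviewing results, investigators determined that a one-sided test with a significance level of 0.10 will be used".

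Section 9.2 (Medications) adds a second adjustment rule: "If we find differences in the use of specific medications between study groups (such as statins or cilostazol), we will adjust for these differences". Medication changes are recorded at monthly visits, and the request not to change drugs is soft: "Participants and their physicians will be asked not to change their medications during the study if possible".

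**The concern.** By stratifying on baseline walk, the plan treats it as prognostic. A change score subtracts baseline with a fixed coefficient of 1. If the true slope of follow-up on baseline is below 1, change remains correlated with baseline and the t interval leaves that variation in the error term. Stratified allocation also makes the arms more alike than the unadjusted standard error assumes, so the test is slightly conservative. Section 11.2 gives estimation of an effect size as one of the pilot's two purposes, alongside feasibility, so the width of this interval matters.

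The conditional route to ANCOVA does not solve this. It searches for chance imbalance, which stratification has largely removed for this one variable, while other characteristics can still enter by chance. With no threshold, no significance level for the screen, no covariate list and no rule on which result is primary, the adjusted model is settled only once data are in hand.

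The medication rule raises a different issue. Drug use after randomisation could be affected by treatment, and adjusting for it could bias the estimated effect. The documents give no basis for quantifying that bias.

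**Working it through.** **Inputs from the plan.** 44 randomised; 40 completers, 20 per arm; margin 0.64 SD, about 33 m (section 11.2); random blocks of 4 and 6 (section 9.1); one-sided 0.10 (section 11.3); small and large meaningful differences of 20 m and 50 m (section 11.2). Eligibility: those walking "less than 500 feet or more than 1600 feet during the baseline six-minute walk will be excluded from the study" (section 9.2).

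**Reproducing the plan's figure.** t(0.975, 38) × √(1/20 + 1/20) = 2.024 × 0.3162 = 0.640 SD. The stated margin is therefore the unadjusted t interval. The implied SD of change is 33/0.640 = 51.5 m, and the SE is 51.5 × 0.3162 = 16.3 m. The one-sided 90% distance is 1.304 × 16.3 = 21.3 m.

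**Assumed correlation.** The baseline to follow-up correlation r is not stated. With equal variances, SD(change)² = 2·SD²·(1 − r), so r = 1 − 51.5²/(2·SD²).
- The window of 500–1600 ft is 152–488 m. Evenly spread, its SD is 335.3/√12 = 96.8 m, which gives r = 0.86.
- An SD of 60 m, assumed as a lower value, gives r = 0.63.

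**ANCOVA.** Under equal variances, SE = 16.3 × √((1 + r)/2), with 37 df (t = 2.026 two-sided 95%; 1.305 one-sided 90%). Power is from the noncentral t at one-sided 0.10. The rows for r = 0.5 and 0.9 lie outside the range derived above and show sensitivity only.

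| r | SE (m) | 95% margin (m) | Narrower by | One-sided 90% distance (m) | Power, 20 m | Power, 50 m |
|---|---|---|---|---|---|---|
| t interval | 16.3 | 33.0 | – | 21.3 | 0.47 | 0.96 |
| 0.5 | 14.1 | 28.6 | 13% | 18.4 | 0.55 | 0.99 |
| 0.63 | 14.7 | 29.8 | 10% | 19.2 | 0.52 | 0.98 |
| 0.7 | 15.0 | 30.5 | 8% | 19.6 | 0.51 | 0.98 |
| 0.8 | 15.5 | 31.3 | 5% | 20.2 | 0.50 | 0.97 |
| 0.86 | 15.7 | 31.8 | 4% | 20.5 | 0.49 | 0.97 |
| 0.9 | 15.9 | 32.2 | 2% | 20.7 | 0.49 | 0.97 |

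**Simulation of the design.** 30,000 trials per setting; 44 randomised in blocks of 4 or 6 within two assumed baseline strata; 40 completing at random.
- *Bias of the t estimate:* within 0.2 m of zero.
- *Mean SE:* 16.2 m for the t analysis, against 14.1, 15.0, 15.5 and 15.9 m for ANCOVA at r = 0.5, 0.7, 0.8 and 0.9. This agrees with the formula.
- *Size of the nominal 0.10 t test:* 0.084, 0.093, 0.094 and 0.097 at the same r with a median split, and 0.086–0.097 with a lower-quartile split. ANCOVA gives 0.099–0.105. Monte Carlo error is about 0.002.
- *Baseline t test on walk distance reaching p < 0.05:* 0.3% of trials (median split) to 0.8% (quartile split), against 5.0% without stratification.

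A separate run of 6,000 trials per setting, with two or three strata, gave 95.9–96.7% coverage for the nominal 95% t interval at r = 0.6–0.7 and close to nominal at r = 0.9.

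**The case against.** The strongest reply is that this is an efficiency preference. The planned interval is unbiased, its stated margin is correct, and it errs on the conservative side, so it creates no false claim of benefit. That stands.

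The size of the gain is also uncertain. Neither r nor the 60 m lower SD comes from the documents, and eligibility truncates the baseline distribution only, so equal variances cannot be taken for granted. The gain really depends on the slope b of follow-up on baseline: the ANCOVA residual variance is 51.5² − (1 − b)²·SD². With SD 60–97 m, a slope of 0.9 gives an interval only 0.6–1.7% narrower, and at 0.95–1 there is practically no gain. That stands too. It argues against claiming a large benefit rather than against adjusting, because the most that can be lost is one degree of freedom (33.03 m against 33.0 m at slope 1).

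The 20 m figure is context only. The plan has no rule comparing the smallest significant difference with 20 m, and section 11.3 bases the decision on a larger trial on all the evidence.

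The trigger percentages rest on assumed strata and an assumed p < 0.05 screen. The screen is most naturally read as one of baseline characteristics, and outcome staff are blinded with lots coded by letter, so it is not selection on the outcome. Discretion over threshold, covariates and the leading result nevertheless remains. The medication rule is a separate matter and does not add weight to the efficiency argument.

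**Conclusion.** The concern holds, as an efficiency and pre-specification point. The primary interval is valid but wider than necessary: about 4–10% if r is 0.63–0.86, 2–13% over the wider range 0.9–0.5, and nothing if the slope is close to 1. These figures assume equal variances, a change SD of 51.5 m and 20 completers per arm. Power for 50 m is already about 0.96, so the practical effect is modest. The ANCOVA trigger is undefined and, with stratification, would very rarely bring in baseline walk. The medication rule, as worded, permits post-randomisation adjustment with a possible bias of unknown size. Because the remedy costs so little, the plan should be changed.

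**What to change.** 1. Pre-specify the primary analysis as ANCOVA of six-month walk (or change) on treatment and continuous baseline six-minute walk, for both the 2.5-hour and the 24-hour comparison.
2. Do the same for each secondary outcome with its own baseline value.
3. Keep the t interval on change as a labelled supportive analysis.
4. Remove baseline significance tests and the imbalance wording as the trigger for adjustment.
5. Restrict any medication adjustment to use at baseline, in a labelled sensitivity analysis.

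The cost is one degree of freedom and an SAP amendment, with no new data. The amendment must be dated before unblinding. It would be a second change to the primary inference after recruitment closed, following section 11.3, so its date and reason should be stated openly.
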